5.2.1 Cardiovascular events

MACE+ events (death, non-fatal MI, non-fatal stroke, heart failure requiring hospitalization and unstable angina leading to hospitalization) should be reported as SAEs in the eCRF and will be adjudicated. Deep vein thrombosis, pulmonary embolism, vascular access thrombosis and hypertensive emergencies will also be reported and adjudicated. SAEs will be screened against a pre-specified list of MedDRA preferred terms to identify potential MACE+ events plus the rest

of the CV events listed above. When a potential CV event is identified, the Principal Investigator will be contacted to collect supporting medical records; once the clinical endpoint packet is compiled, blinded adjudication of candidate CV events will be conducted by the Independent Endpoint Review Committee (IERC) as described in the IERC charter.

Independent Event Review Committee Charter (IERC) contains complete information regarding the cardiovascular events and criteria for adjudication.

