1.4 Study Design

This is a Phase 3, multicenter, randomized, open-label, active-controlled study to evaluate the efficacy and safety of roxadustat compared to epoetin alfa for the treatment of anemia due to CKD in dialysis patients (hemodialysis or peritoneal dialysis). This study is planned to randomize approximately 2000 patients from approximately 250 centers worldwide.

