6.2 Definitions of serious adverse event

A serious adverse event is an AE occurring during any study phase (i.e., screening, treatment and follow-up), that fulfils one or more of the following criteria:

- Results in death
- Is immediately life-threatening
- Requires in-patient hospitalisation or prolongation of existing hospitalisation
- Results in persistent or significant disability/incapacity or substantial disruption of the ability to conduct normal life functions
- Is a congenital abnormality or birth defect
- Is an important medical event that may jeopardise the subject or may require medical intervention to prevent one of the outcomes listed above.

For further guidance on the definition of a SAE, see [Appendix B](#) to the Clinical Study Protocol.

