Appendix B Additional Safety Information

Further Guidance on the Definition of a Serious Adverse Event (SAE)

Life threatening

‘Life-threatening’ means that the subject was at immediate risk of death from the AE as it occurred or it is suspected that use or continued use of the product would result in the subject’s death. ‘Life-threatening’ does not mean that had an AE occurred in a more severe form it might have caused death (eg, hepatitis that resolved without hepatic failure).

Hospitalisation

Outpatient treatment in an emergency room is not in itself a serious AE, although the reasons for it may be (eg, bronchospasm, laryngeal oedema). Hospital admissions and/or surgical operations planned before or during a study are not considered AEs if the illness or disease existed before the subject was enrolled in the study, provided that it did not deteriorate in an unexpected way during the study.

Important medical event or medical intervention

Medical and scientific judgement should be exercised in deciding whether a case is serious in situations where important medical events may not be immediately life threatening or result in death, hospitalisation, disability or incapacity but may jeopardize the subject or may require medical intervention to prevent one or more outcomes listed in the definition of serious.

These should usually be considered as serious.

Simply stopping the suspect drug does not mean that it is an important medical event; medical judgement must be used.

- Angioedema not severe enough to require intubation but requiring iv hydrocortisone treatment
- Hepatotoxicity caused by paracetamol (acetaminophen) overdose requiring treatment with N-acetylcysteine
- Intensive treatment in an emergency room or at home for allergic bronchospasm
- Blood dyscrasias (eg, neutropenia or anaemia requiring blood transfusion, etc) or convulsions that do not result in hospitalisation

Development of drug dependency or drug abuse

A GUIDE TO INTERPRETING THE CAUSALITY QUESTION

When making an assessment of causality consider the following factors when deciding if there is a ‘reasonable possibility’ that an AE may have been caused by the drug.

- Time Course. Exposure to suspect drug. Has the subject actually received the suspect drug? Did the AE occur in a reasonable temporal relationship to the administration of the suspect drug?

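### The central term screen for adjudicated CV events covers SAEs only, so non-serious DVT, PE, vascular access thrombosis and hypertensive emergency reach the blinded committee only if the open-label site flags them

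*Protocol*

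**What the plan says.** Protocol 5.2.1 treats two groups of events differently.

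- **MACE+ components.** The sentence listing them ends "unstable angina leading to hospitalization) should be reported as SAEs in the eCRF and will be adjudicated".
- **The other four types.** "Deep vein thrombosis, pulmonary embolism, vascular access thrombosis and hypertensive emergencies will also be reported and adjudicated". Nothing is said about seriousness.

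The section then describes one central identification step for both groups: "SAEs will be screened against a pre-specified list of MedDRA preferred terms to identify potential MACE+ events plus the rest" of the CV events just listed. Once a candidate is identified, the investigator is asked for records, and "blinded adjudication of candidate CV events will be conducted by the Independent Endpoint Review Committee (IERC) as described in the IERC charter".

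Seriousness follows the general criteria in Protocol 6.2, such as "Requires in-patient hospitalisation or prolongation of existing hospitalisation" or being an important medical event. Appendix B adds: "Outpatient treatment in an emergency room is not in itself a serious AE, although the reasons for it may be". Neither place makes any of the four types serious by definition.

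On knowledge of treatment, Protocol 1.4 states: "This is a Phase 3, multicenter, randomized, open-label, active-controlled study to evaluate the efficacy and safety of roxadustat compared to epoetin alfa". Protocol 8.5 commits to adjudicating the events described in 5.2.1, which include these four. SAP 3.3 refers to the IERC charter and the pooled plan and adds no method of identification.

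**The concern.** The commitment to adjudicate is wider than the step meant to find the cases. A clotted access cleared the same day, or a DVT managed without admission, may be entered as a non-serious AE. If so, its preferred term is not in the data being screened, and the case goes forward only if the site recognises it as a potential endpoint and says so.

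The primary safety objective is to contribute adjudicated CV data to the pooled analyses. Site staff know the treatment arm. The committee does not, but it can judge only the cases it receives. If sites flag non-serious cases less than fully, counts of the four types are too low. If they flag them at different rates by arm, the comparison is biased, and blinded adjudication cannot repair that.

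**Working it through.** No sample size, power, alpha or event count in the documents depends on this point, so there is no figure to reproduce. The check has two parts.

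**1. Routes to adjudication for a non-serious case of the four types**

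| Route | Where | Covers a non-serious case? | Who triggers it |
|---|---|---|---|
| Preferred-term screen | Protocol 5.2.1 | No, SAEs only | Central |
| Report as an event to be adjudicated | Protocol 5.2.1 | Yes | Site |
| Capture of potential endpoints after stopping study drug | Protocol 3.9.3.2 | Yes | Site |
| Telephone contact if the EOS visit is missed | Protocol 3.9.3.5 | Yes | Site |
| EQ-5D-5L after a suspected event | Protocol Table 1, footnote k | Prompt only | Site |
| Hospitalization and emergency-room data at each visit | Protocol 5.3.2 | Recorded, but no link to adjudication is described | Site |

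Every route open to a non-serious case starts at the site. The only central one excludes it.

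Does the protocol intend the four types to be SAEs? The contrast between the two sentences in 5.2.1 suggests not. Sections 3.9.3.2 and 3.9.3.5 name these events alongside SAEs as separate items. That is weaker evidence, because the same lists also contain MACE+ events, which are SAEs.

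**2. Illustration of size (assumed inputs)**

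Let f be the share of the four event types that is non-serious, and q the probability that a site flags a non-serious case. The documents give neither.

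Captured share in an arm = (1 − f) + f·q.

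Observed ratio when the true ratio is 1.00 = [(1 − f) + f·q₁] / [(1 − f) + f·q₂].

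| f | No flagging in either arm: captured | 80% vs 60%: ratio | 100% vs 50%: ratio |
|---|---|---|---|
| 0% | 100% | 1.00 | 1.00 |
| 10% | 90% | 0.98/0.96 = 1.02 | 1.00/0.95 = 1.05 |
| 30% | 70% | 0.94/0.88 = 1.07 | 1.00/0.85 = 1.18 |
| 50% | 50% | 0.90/0.80 = 1.13 | 1.00/0.75 = 1.33 |

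Either arm could be the one flagged more often, so the inverses (about 0.98 down to 0.75) are equally possible. With equal flagging the ratio stays at 1.00 and only the counts fall: at q = 50% in both arms, capture is 95%, 85% and 75% for f = 10%, 30% and 50%.

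**The case against.** The strongest reply is that the SAE screen is a backstop and site reporting is the main route. Section 5.2.1 tells sites without condition that the four types are reported and adjudicated, and three other places remind them of these events. That stands. A reader might infer that candidates are found only by screening SAEs, or that non-serious cases can never reach the committee. The documents do not support either inference.

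Second, the word for also in 5.2.1 follows directly on the SAE requirement and could be read as extending it to the four types. That reading would close the gap. It is possible, but the text does not state it.

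Third, a reader might infer that outpatient treatment makes a case non-serious. It does not. Appendix B allows that the reason for the treatment may be serious, and says important medical events should usually be considered so. Many outpatient cases may therefore be SAEs. Even so, whether a case counts as an important medical event is a judgement, made by staff who know the arm, and that judgement decides whether the case enters the screen.

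Fourth, Protocol 5.2.1 points to the IERC charter for complete information on the CV events, and Protocol 6.8.2 leaves committee procedures to it. The charter may describe a wider screen. This limits the finding to the protocol and SAP as written.

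Fifth, none of the four types belongs to MACE or MACE+, this SAP analyses no CV endpoint (SAP 4.3.1), and non-serious cases within the treatment-emergent window would still appear in the AE tables (SAP 4.3.8.1). That limits importance, but AE tables do not replace the adjudication promised in Protocol 8.5.

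**Conclusion.** The point holds in a limited form. For DVT, PE, vascular access thrombosis and hypertensive emergency, the only central identification step in the protocol and SAP misses non-serious cases, and those cases depend on flagging by an open-label site. Ascertainment of these four types may be incomplete and could differ by arm.

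Two stronger conclusions are not supported. A reader might infer that the pooled MACE or MACE+ result is compromised. It is not on this ground: those components must be reported as SAEs, so they fall within the screen, and the 611-subject MACE target is untouched. A reader might also take the ratios of 1.02 to 1.33 as an estimate of bias. They are not. They rest on assumed non-serious shares of 10% to 50% and assumed flagging differences, and the documents show no evidence that flagging differs by arm. If every case is serious there is no loss, and if flagging is equal there is no ratio bias.

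This is a cheap improvement worth making, not a flaw that invalidates the safety data. It falls away if the charter already screens all AEs.

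**What to change.** In Protocol 5.2.1, state that for the four event types the preferred-term screen is applied to all AEs, serious and non-serious. Run it on the coded AE database before lock, by staff without access to treatment arm. Send the additional candidates through the existing IERC process, and report the number of candidates by source (site report, SAE screen, non-serious AE screen) and by arm. That table would show whether flagging differed. If the charter already provides for such a screen, a sentence in 5.2.1 saying so is enough.

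The data are largely in hand: AEs are collected from first dose (Protocol 6.3.1) and MedDRA-coded (Protocol 9.4). Protocol version 8.0 is dated 19 September 2018 and the study is estimated to end by Q3 2018, so a data step before lock is more practical than a change in site procedure.

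The cost is one program run, extra record requests and extra adjudication packets. Counts of these events may rise in both arms.

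Two limits remain. The screen still depends on the site having recorded the AE; capture is complete, with a ratio of 1.00 for any f, only if every matching AE was entered. And for subjects on modified follow-up more than 28 days after stopping study drug, Protocol 3.9.3.2 asks for SAEs and endpoint-related information but not all AEs, so a non-serious case there would still depend on the site.

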5.2.2 Laboratory assessments

Blood samples for determination of clinical chemistry, hematology, lipid panel, serology, vitamin B12, folate and serum iron profile will be taken at the times indicated in [Table 1](#) and analyzed by Covance Central Laboratory Services.

Additional safety samples may be collected if clinically indicated at the discretion of the Investigator.

The following laboratory variables will be measured (blood, serum or plasma will be specified in the laboratory manual):

Table 2 Laboratory Safety Variables

Hematology/Hemostasis	Clinical Chemistry
Hemoglobin (Hb)	Creatinine
Hematocrit	Creatinine kinase
Leukocyte count	Bilirubin, total
Leukocyte differential count (absolute count)	Alkaline phosphatase (ALP)
Platelet count	Aspartate aminotransferase (AST)
	Alanine aminotransferase (ALT)
Serology	Gamma-glutamyl transferase (GGT)
Hepatitis B surface antigen	Albumin
Hepatitis C antibody	Potassium
Human immunodeficiency virus (HIV)	Calcium, total
	Sodium
Additional Laboratory Analyses	Chloride
Vitamin B12	Magnesium
Folate	Bicarbonate
Intact Parathyroid hormone (iPTH)	Phosphorus
hsCRP*, hepcidin*	Glucose
Lipid Panel	Uric Acid

Total cholesterol

HDL

Triglycerides

Calculated low-density lipoprotein (LDL)

Total protein

Lactate dehydrogenase

Blood urea nitrogen

Serum hCG pregnancy test

Iron Profile

Iron

Ferritin

Total iron binding capacity (TIBC)

Transferrin saturation (TSAT)

* = will be analysed from specimens obtained in subjects who consent to biobanking blood samples

The Investigator should make an assessment of the available results with regard to clinically relevant abnormalities. The laboratory results should be signed and dated and retained at centre as source data for laboratory variables. For information on how AEs based on laboratory tests should be recorded and reported, see Section 6.3.

Note: In case a patient shows an AST **or** ALT $\geq 3 \times \text{ULN}$ **or** total bilirubin $\geq 2 \times \text{ULN}$ please refer to [Appendix D](#) ‘Actions required in cases of combined increase of Aminotransferase and Total Bilirubin - Hy’s Law’, for further instructions.

Additional laboratory assessments performed for purposes other than general safety evaluation are also listed in [Table 2](#)

5.2.3 Physical examination

A **comprehensive** physical examination will be conducted according to the Study Plan, [Table 1](#), and recorded in the source documents. This examination will include general appearance and the following body regions and systems: General appearance, skin, head and neck, lymph nodes, thyroid, musculoskeletal/extremities, cardiovascular, respiratory, abdomen, neurological and any other, if deemed necessary.

Height is measured only at screening. Weight is recorded at screening, randomization visit, and then at specific time points as described in the Study Plan, [Table 1](#). A **targeted** physical examination (general appearance, cardiovascular, respiratory and abdomen) will be conducted throughout the study as described in the Study Plan, [Table 1](#).

Any clinically relevant adverse change will be recorded as an AE in the eCRF (see Section [6.3.6](#)).

5.2.4 ECG

5.2.4.1 Resting 12-lead ECG

Standard 12-lead ECGs will be performed on all patients at specific time points as described in the Study Plan, [Table 1](#), as to local routines. A single ECG will be taken after the patient has been resting in the supine position for 5 minutes. Any abnormalities must be evaluated in clinical context (based on patient's medical history and concomitant medication) and the investigator should determine if it is clinically significant. Clinically significant abnormalities should be reported as an AE.

Only the visit, ECG date, heart rate (HR), RR Interval, PR Interval, QRS Interval, QT Interval, overall interpretation and relevant comments will be recorded in the eCRF. ECG recordings will be kept as source documents.

5.2.5 Vital signs

The vital signs, blood pressure and heart rate, will be assessed at the visits as described in the Study Plan, [Table 1](#) and recorded in the eCRF.

5.2.5.1 Heart rate and blood pressure

At most visits, HR and BP will be measured according to usual clinical practice and recorded.

On specific visits indicated in [Table 1](#), HR and BP will be measured in triplicate after the patient has been comfortably at rest in a seated position for at least 5 min. The position of the patient should be comfortable with the arm where the blood pressure is recorded to be within the level of heart (the middle of the cuff on the upper arm is at the level of the right atrium (the midpoint of the sternum)). The patient will be instructed to relax as much as possible and to not talk during the measurement procedure. Preferably measurement will be done with an electronic automated oscillometric device. The same device should preferably be used for the patient during the course of the study and in the same arm. Blood pressure will be measured in triplicate with at least one-minute intervals between measurements. In HD patients BP and HR will be assessed prior to initiation of the dialysis procedures. In peritoneal dialysis (PD) patients BP and HR will be assessed when they come to the clinic. All the three readings will be reported in the eCRF.

The heart rate will be assessed by pulse palpation of radial artery for 30 s immediately after each recording of the blood pressure. It could be also performed with an oscillometric device if this is used for blood pressure measurement. The triplicate heart rate assessments will recorded in the eCRF.

Blood pressure measurements are to be obtained prior to initiation of each dialysis procedure.

5.3 Other assessments

5.3.1 Patient reported outcomes

All study patients will be asked to complete the Euro Quality of life (QoL) Health Utility Index questionnaire at time points indicated in the Study Plan, [Table 1](#). The questionnaires should be completed by the patient prior any other intervention.

5.3.1.1 EuroQol Health Utility Index – EQ-5D-5L

The EQ-5D-5L is a self-reported questionnaire measuring utility values. The EQ-5D consists of the EQ-5D descriptive system and the EQ visual analogue scale (VAS). The EQ-5D descriptive system comprises 5 dimensions of health: mobility; self-care; usual activities; pain/discomfort; and anxiety/depression. Each dimension has 5 levels: no problems, slight problems, moderate problems, severe problems, and extreme problems. The VAS records the respondent's self-rated health status on a graduated (0-100) scale, where the endpoints are labeled 'Best imaginable health state' and 'worst imaginable health state' with higher scores for higher HRQoL. EQ 5D health states, defined by the EQ-5D descriptive system, may be converted into a single summary index by applying a formula that essentially attaches values (also called weights) to each of the levels in each dimension. The index can range from 1 for full health to 0 for being dead, but it can also be below 0 indicating a health state worse than being dead.

5.3.1.2 Administration of patient-reported outcome

All patient-reported outcomes (PROs) are paper-based and will be administered at baseline and according to Study plan, [Table 1](#) and recorded in the eCRF.

Each center must allocate the responsibility for the administration of the questionnaire to a specific individual (e.g., a research nurse, study coordinator) and if possible assign a back-up person to cover if that individual is absent. The AstraZeneca Study Team (or delegate) will provide relevant training in administration of the questionnaire. The significance and relevance of the data need to be explained carefully to participating patients so that they are motivated to comply with data collection.

The instructions for completion of the PRO questionnaire are as follows:

- The EQ-5D-5L must be completed prior to any other study procedures (following Informed Consent) and before discussion of disease progress to avoid biasing the patient's responses to the questions. They must be completed in private by the patient
- The patient should be given sufficient time to complete at their own speed
- The patient should not receive help from relatives, friends or clinic staff to answer the questionnaire. However, if the patient is unable to read the questionnaire (e.g. is visually impaired) the questionnaire may be read out by trained clinic staff and responses recorded
- On completion of the questionnaire it should be handed back to the person responsible for questionnaire who should check for completeness
- Only one answer should be recorded for each question

5.3.2 Hospitalizations

Details on hospitalizations (including emergency room/skilled nursing facility use) will be collected at each study visit. Reason, admission, discharge dates and type and reason for hospitalization will be recorded in the eCRF. Details on hospitalizations will also be collected at

follow-up visits in patients who prematurely discontinued treatment (only if they have taken at least one dose of study drug), until the projected date of the EOS visit.

5.4 Pharmacokinetics

5.4.1 Collection of samples

Venous blood samples (4 mL) for determination of roxadustat concentration in plasma will be collected at week 4 and week 8, only for patients taking roxadustat. Patients will be instructed **NOT** to take the study medication on the day of week 4 visit (not necessary for week 8). If a dose of the study medication is scheduled for that day, the dose can be given **AFTER** the collection of the blood sample. For both visits the date and time of sample collection will be recorded as well as the last dosing date and time of study medication.

Samples will be collected into appropriately labelled tubes containing sodium-heparin as anticoagulant. Immediately after collection, blood samples will be kept on melting ice until ready for centrifugation, which must be done within 30 minutes of collection. Blood samples will be centrifuged at 1500 g for 10 minutes at room temperature in order to obtain plasma. Plasma will be harvested and transferred into an appropriately labelled amber polypropylene storage tube and stored at -20°C or below, within 30 minutes of centrifugation. Samples will be stored frozen at the site until shipment. Samples will be sent to the central laboratory packed with sufficient dry ice to keep the samples frozen. All applicable shipping regulations will be followed. Further details will be provided in the laboratory manual.

